1.0 PROTOCOL SYNOPSIS

Title	A Prospective Blinded Within-Subject Randomized Controlled Clinical Study to Investigate the Safety and Effectiveness of RECELL for Repigmentation of Stable Vitiligo Lesions
Protocol No.	CTP009
Phase of Study	Pivotal Study
Proposed Indication for Use	The RECELL [®] Autologous Cell Harvesting Device is intended for use at the patient's point-of-care for the safe and rapid preparation of Spray-On Skin [™] Cells from a small sample of a patient's own skin. The cell suspension prepared using the RECELL System is suitable for application to a prepared treatment area for repigmentation of stable vitiligo lesions.
Primary Objective	To evaluate the application of Spray-On Skin [™] Cells, prepared using the RECELL® Device, for safe and effective repigmentation of ablated stable vitiligo lesions.
Study Population	Pivotal Cohort The pivotal cohort will consist of no fewer than 23 subjects. This study utilizes an adaptive design with an interim analysis planned for the purposes of sample size re-estimation (to achieve adequate conditional power). There will be a maximum of 46 subjects in the pivotal cohort.
	Roll-in Cohort Up to two roll-in cohort patients may be randomized at each investigational site for purposes of ensuring proficiency with the investigational device and study procedures prior to advancing to enrollment in the pivotal cohort. Any subject randomized prior to Rev 3 of the investigational plan will be considered a roll-in cohort subject. All roll-in subjects must meet the same eligibility criteria, will undergo the same study procedures and follow-up assessments as the pivotal cohort subjects; however, data from the roll-in cohort of subjects will be analyzed separately from the pivotal cohort. A maximum of 35 subjects total roll-in cohort subjects (including those randomized prior to Rev 3) are anticipated in addition to the planned pivotal cohort subjects. Subjects in the roll-in cohort may not re-enroll in the pivotal cohort.
	There will be a maximum of 81 subjects from both cohorts.
Number of Trial Centers	The study will be executed at no more than 15 centers in the United States.
Clinical Justification/Clinical Benefit	The RECELL® Autologous Cell Harvesting Device has been safely and effectively used to prepare and apply cell suspension that includes pigment-producing cells (melanocytes) for treatment of burn wounds. Patients without functional melanocytes and who are candidates for application of skin cells to depigmented areas of skin may benefit from point of care use of the RECELL Device.
Investigational Treatment	Skin cell suspension at 1:20 expansion ratio (donor area : recipient area), prepared using the RECELL System, will be applied to an ablated (de-epithelialized) area of depigmentation, followed by targeted phototherapy using NB-UVB.
Control	Each subject will serve as their own Control, with a depigmented area receiving no RECELL treatment but receiving the same targeted NB-UVB as the investigational treatment area.

Study Design	This is a prospective blinded randomized within-subject controlled study to evaluate the clinical performance of RECELL for repigmentation of stable, depigmented lesions in subjects 18 years or greater. The trial will evaluate matched pairs of stable depigmented study areas. After identification of two study areas, one study area will be randomly assigned to RECELL, and the other will serve as the Control.	
	Follow-up visits during the effectiveness period will be at Weeks 1, 4, 12 and 24 post-treatment followed by a durability period that will include follow-up visits at Weeks 36 and 52 post-treatment. Acute healing, pigmentation, and compliance with phototherapy will be evaluated. Treatment-related and serious adverse events will be documented throughout the duration of the study. For all study subjects and visits, study areas will be documented using standardized digital photography.	
	Pigmentation of all study areas will be determined via centralized image interpretation by an expert dermatological panel blinded to treatment allocation (i.e., Central Review Committee, CRC) to decrease variability. In addition to the CRC, an assessment of pigmentation and study area Vitiligo Area Scoring Index (VASI) will be performed by the investigator for each study area. To assess durability of responding RECELL-treated study areas at Week 52, the investigator and the CRC will confirm that ≥ 80% of the pigmentation remains relative to the subject's Week 24 photograph.	
	Patient reported outcomes will be captured using the Vitiligo Noticeability Scale (VNS), Patient Global Impression of Change-Vitiligo (PaGIC-V), and a subject global treatment success assessment.	
	After completion of the Week 24 (non-responders) or Week 52 (responders) visit, the subject may be given the option for RECELL treatment of their depigmented study area(s).	
Primary Effectiveness Endpoint	The primary effectiveness endpoint is the proportion of Responders for RECELL-treated areas versus Control at Week 24. Responders are defined as study areas achieving ≥ 80% pigmentation as determined by the Central Review Committee.	
Secondary Effectiveness Endpoints	 Central Review Committee categorization of repigmentation (0-25%, 26-50%, 51-79% and 80-100%) at Week 24 Central Review Committee assessment of color matching for the study areas at Week 24 	
Tertiary (Exploratory) Measures	 Subject and investigator global treatment success and donor site satisfaction Subject-reported Vitiligo Noticeability Score vs baseline (based on photographs) Investigator assessment of pigmentation responder (≥ 80% pigmentation) for the study areas at Week 24 Investigator assessment of repigmentation category (ordinal data) for the study areas CRC and investigator assessment of pigmentation for the study areas at Weeks 36 and 52 Investigator study area VASI scores, change from baseline Investigator assessment of color matching for the study areas CRC assessment of color matching for the study areas at Weeks 36 and 52 Patient Global Impression of Change-Vitiligo (PaGIC-V) Repigmentation durability at Week 52 as assessed by the investigator and CRC 	

Safety Evaluations	Safety will be evaluated in terms of healing and scar outcomes, and treatment-related adverse events.
	Safety variables that will be evaluated at the study areas and donor sites: 1. Incomplete healing (<100%) at Week 4 2. Infection 3. Koebnerization 4. Donor and recipient site scar requiring surgical treatment 5. Milia requiring medical intervention 6. Other treatment-related and serious adverse events
Inclusion Criteria	 Subjects must meet all the following criteria to be eligible: Focal, segmental or generalized (i.e., nonsegmental) stable vitiligo, defined as no new depigmented areas nor any depigmented areas that have expanded in size within the preceding 12 months, regardless of whether the areas are intended to be used as study areas. Photo documentation (current and at least 12 months prior) of the patient's depigmented areas have been evaluated as stable by an independent Screening Committee. The patient has not undergone topical treatment (e.g., steroids, tacrolimus) for the study areas within the past 90 days. The patient has not undergone phototherapy (e.g., NB-UVB) for the study areas within the past 90 days. The patient is a candidate for surgical intervention of a depigmented area, defined as a patient who has previously been compliant with but has not satisfactorily responded to both:

Exclusion Criteria	 Subjects who meet any of the following criteria are not eligible: The study areas selected have concomitant dermatologic conditions other than vitiligo. The study area selected for treatment includes the lips, eyelids, plantar surface of feet, palmar surface of hands, fingertips, wrists, ankles, elbows, or knees. The patient is unable to undergo the treatment area preparation. Patients who are pregnant. Patients with any of the following: universalis vitiligo, depigmented areas over >30% of their body surface area, depigmented lips and fingertips (lip-tip vitiligo), or 3 depigmented fingertips, defined as depigmentation of the dorsal aspect of the fingertip from the distal interphalangeal joint to the tip of the digit.
	6. Patients with recent history (within previous 12 months) of: a. Koebnerization, b. confetti-like, or c. trichrome lesions. 7. Patients with a history of keloid formation. 8. Patients who have used a tanning salon in the past 60 days. 9. The patient has other concurrent conditions that in the opinion of the investigator may compromise patient safety or study objectives. 10. Current use of medications (e.g., anticoagulants such as heparin or warfarin) that in the investigator's opinion may compromise patient safety or trial objectives. 11. The patient has a known hypersensitivity to trypsin or compound sodium lactate for irrigation (Hartmann's) solution. 12. Life expectancy is less than 1 year.
Study-specific procedure highlights	 Two depigmented study areas will be outlined and labeled (A and B). Randomization to assign area A or B to RECELL will be performed in the EDC. Donor skin will be harvested under local anesthetic sufficient to prepare suspension for both the recipient and donor sites. The RECELL-assigned study area will be ablated to a sufficient depth to remove the epidermis and expose the papillary dermis. Spray-On SkinTM Cells will be applied to the RECELL-assigned study area using a 1:20 expansion ratio. Standardized dressings will be applied to the RECELL-treated study area and donor site. NB-UVB phototherapy will commence on both study areas after dressings are no longer in place.

Screening Committee (SC)

Post-consent and prior to randomization, investigational sites must submit photographic evidence (with date stamp or other evidence of date of image acquisition) of stable vitiligo for each subject that includes:

- 1) Current photos of the subject's depigmented areas obtained during screening
- Current photos of the subject's dorsal hands displaying all fingertips obtained during screening
- 3) Historic photos \geq 12 months prior of the subject's depigmented areas

The independent SC will consist of a minimum of 3 board-certified dermatologists. Each patient being considered for treatment will have the photographic evidence outlined above in addition to other relevant medical history reviewed by a minimum of 3 committee members. Two (2) of 3 members must concur the photographs are of stable vitiligo prior to the investigational site proceeding with randomization and treatment. The SC will be blinded to which investigational site the photographs originated from.

Central Review Committee (CRC)

Three independent board-certified dermatologists (Central Review Committee, CRC) will be selected based on specific selection criteria for the purpose of providing blinded adjudication to determine whether successful repigmentation of the study areas (≥ 80%) have been achieved and if not, then to determine categorization of repigmentation. The CRC will be blinded to the study site, treatment assignment, and the investigator's determination of repigmentation for each study area. The adjudicated results will be used in the primary analysis.

The CRC will be governed under a charter that will be approved by the committee, and that will contain the guidance and rules under which they will review and adjudicate data. Assessments of repigmentation at 24 weeks post- treatment (relative to baseline) will be assessed by all three members of the CRC. If two CRC members agree, adjudication of that subject's timepoint will be deemed complete. If there are any discordant cases (i.e., agreement not achieved between two CRC members), the committee will review the case together with the majority ruling (2/3 CRC members in agreement) serving as the final adjudication. The CRC members will record their review independently. Panel assessments will be conducted consistent with consensus guidance published by the Vitiligo Global Issues Consensus Group (VGICG) for the evaluation of patients with vitiligo using a reference atlas developed by the VGICG depicting vitiligo repigmentation patterns and color match.

Statistical considerations

The sample size for this trial was determined based on the primary effectiveness endpoint of responders at 24 weeks. The trial is designed to test if RECELL treatment using an expansion ratio of 1:20 is superior to Control. An alpha level of 0.025 is utilized for hypothesis testing. The trial will incorporate an unblinded interim analysis for purposes of sample size re-estimation after approximately half the planned subjects reach 24 weeks. The interim analysis will be conducted according to the promising zone method of Mehta and Pocock (2011), allowing for up to twice the original planned sample size.

Assuming 5% responders in Control and 60% responders for RECELL, 20 subjects yields 90% power, one-sided 0.025 level of significance to demonstrate RECELL superiority versus Control. This assumes a 10% superiority margin relative to Control.

Anticipating 10% lost to follow-up, 23 subjects are planned. An interim analysis for purposes of sample size re-estimation will occur when 11 subjects have 24-week follow-up data. The sample size may be increased based on the results of this interim analysis to a maximum of 46 subjects.

Note that it is possible that, depending on rate of subject accrual, the interim analysis of 24-week data may not occur until after 23 subjects have already been enrolled.

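### Non-serious local adverse events outside five named variables are documented only if judged treatment-related, and no blinded review of that judgement is described

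*Combined protocol and SAP*

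**What the plan says.** The Study Design row of the synopsis gives the collection rule: "Treatment-related and serious adverse events will be documented throughout the duration of the study". The Safety Evaluations row describes the assessment in matching terms: "Safety will be evaluated in terms of healing and scar outcomes, and treatment-related adverse events".

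That row then lists what is assessed: "Safety variables that will be evaluated at the study areas and donor sites: 1. Incomplete healing (<100%) at Week 4 2. Infection 3. Koebnerization", followed by "4. Donor and recipient site scar requiring surgical treatment 5. Milia requiring medical intervention 6. Other treatment-related and serious adverse events". Items 1 to 5 carry no stated relatedness condition. Item 6, which takes in everything else, is limited to related or serious events.

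Safety is part of the primary objective, which concerns use of the cell suspension "for safe and effective repigmentation of ablated stable vitiligo lesions".

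The study areas are also photographed throughout: "For all study subjects and visits, study areas will be documented using standardized digital photography". The Central Review Committee (CRC) is blinded to treatment assignment, but its stated purpose is "providing blinded adjudication to determine whether successful repigmentation of the study areas" (with categorization and color matching). No role in safety or in attribution is described for it.

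**The concern.** A within-subject design gives each subject a concurrent control for local harms: two matched areas, both receiving targeted NB-UVB, only one receiving RECELL. That comparison is sound if events at both areas are captured in the same way. Here capture of a residual event depends on a causal judgement made before it is written down.

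Two things follow. Events judged unrelated are not documented, so the rate of residual events can be understated. If the judgement is made more readily for one area than for the other, the recorded difference between areas partly reflects attribution rather than harm. A recorded event can be reclassified at analysis. An unrecorded event that left no visible trace cannot be recovered. In a pivotal study with safety in its primary objective, this matters even though it touches only part of the safety data.

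**Working it through.** **Step 1: what the rule covers.** No figure in the plan tests this point, so the first check is a side-by-side reading.

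- Named local variables (Safety Evaluations, items 1 to 5): healing not complete at Week 4, infection, Koebnerization, scars needing surgery, milia needing medical treatment. No relatedness condition is stated. The word that opens item 6 could imply that items 1 to 5 are themselves counted as treatment-related; the text does not settle this.
- Serious events: documented regardless of relatedness.
- Non-serious events not on the list: documented only if treatment-related (Study Design; Safety Evaluations, item 6). No sentence in the synopsis provides for recording them otherwise.
- Scars and milia below the item 4 and 5 cut-offs: these are severity thresholds, a separate matter from attribution. Safety Evaluations also refers to scar outcomes in general.

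**Step 2: is the judgement protected?** Study-specific procedure highlights apply ablation, cell suspension and a dressing to the RECELL-assigned area. The Control row gives the other area NB-UVB without RECELL. Site staff can therefore tell the areas apart. The CRC is the only body stated to be blinded to assignment. The assessor of relatedness is not named, and treatment-related is not defined for the Control area.

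**Step 3: loss of events (assumed rates).** Let p be the true per-subject rate of one residual event at the RECELL area, s the share judged related, and n the number of subjects. Subjects are taken as independent and fully followed.

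P(at least one recorded) = 1 − (1 − p·s)^n

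From the plan: n = 23 (planned) and n = 46 (pivotal maximum). Assumed: p and s.

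For p = 0.10, n = 23:
- s = 1: 1 − 0.90^23 = 0.911
- s = 0.75: 1 − 0.925^23 = 0.834
- s = 0.50: 1 − 0.95^23 = 0.693
- s = 0.25: 1 − 0.975^23 = 0.441

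The range:

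| p | n | s = 1 | s = 0.75 | s = 0.50 | s = 0.25 |
|---|---|---|---|---|---|
| 5% | 23 | 69.3% | 58.5% | 44.1% | 25.1% |
| 5% | 46 | 90.6% | 82.8% | 68.8% | 43.9% |
| 10% | 23 | 91.1% | 83.4% | 69.3% | 44.1% |
| 10% | 46 | 99.2% | 97.2% | 90.6% | 68.8% |
| 20% | 23 | 99.4% | 97.6% | 91.1% | 69.3% |
| 20% | 46 | >99.9% | 99.9% | 99.2% | 90.6% |

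The recorded rate itself is p·s: a true 10% with half attributed is recorded as 5%.

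**Step 4: distortion between areas (assumed shares).** With the same true rate p at both areas and attributed shares s_T (RECELL) and s_C (Control), the recorded difference is p·(s_T − s_C).

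- p = 0.10, s_T = 0.9, s_C = 0.5: 0.10 × 0.4 = +4 points
- p = 0.10, s_T = 0.5, s_C = 0.9: 0.10 × (−0.4) = −4 points

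The true difference is zero in both cases, so the sign depends entirely on how attribution is made.

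**The case against.** The strongest reply is that the main expected local harms are collected anyway. The five named variables have no stated relatedness test, so a reader who infers that attribution filters the local safety data as a whole goes beyond the text. This stands: the filter acts on the residual category.

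Second, photographs at every visit allow visible changes to be re-read later, so it is too much to infer that every unrecorded event is lost for good. This stands in part. The photography sentence covers study areas and not donor sites. Visits are at Weeks 1, 4, 12, 24, 36 and 52, up to 16 weeks apart. Images do not show pain or pruritus and may miss transient events between visits. No blinded safety reading of them is described.

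Third, it is tempting to treat it as established that unblinded site staff make the attribution. The documents do not say who does. That staff can tell the areas apart is a sound inference; that they are the assessors is likely but unstated.

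Fourth, the probabilities rest on assumed rates and weaken with more subjects. At 10% with half attributed, all 81 subjects in both cohorts would still give 1 − 0.95^81 = 98%, although roll-in data are analyzed separately. This is fair as to detecting at least one event. It does not restore the rate, which would still be recorded at half its true value.

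Finally, the text relied on here is the synopsis, and its sentence does not itself contain the word only. If a fuller adverse-event section records all events, the two must be reconciled. Nothing in the synopsis points that way, and Safety Evaluations repeats the restriction.

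**Conclusion.** The point holds for non-serious adverse events outside the five named variables: as written, they are documented only if judged treatment-related. The assessor is not named, no blinded review is described, and the plan leaves open whether NB-UVB effects on the Control area count.

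Omission can only lower the recorded rate of these events. The effect on the comparison between areas has no known direction. A reader might infer that the rule flatters RECELL, but readier attribution at the ablated area would overstate its harms instead, and the documents give no basis for choosing.

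On the assumed 10% rate, the chance of recording at least one event in 23 subjects falls from 91% to between 83% and 44% as the attributed share goes from 75% to 25%; in 46 subjects, from 99% to between 97% and 69%. A 40-point gap in attribution between areas creates a spurious 4-point difference. These figures illustrate the mechanism and are not estimates for this trial. The sample size and the primary effectiveness analysis are unaffected. The change should be made, because it decides which safety data will exist.

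**What to change.** - Record every adverse event at either study area or at the donor site, and every serious event anywhere, regardless of presumed relationship.
- Capture relatedness as a separate field with the options RECELL procedure, NB-UVB and unrelated, and state who completes it.
- Tabulate local events by study area within subject, once for all events and once for related events.

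The cost is a short change to the protocol text, one field on the adverse-event form, and slightly more data entry in at most 81 subjects at no more than 15 centers. The event listing will be longer and may look less favourable. The synopsis mentions subjects randomized before Rev 3, so enrolment may have begun. If so, subjects followed under the present rule should be flagged and their events tabulated separately, because capture would differ between the two groups.

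### The Week 52 CRC durability read is defined by treatment assignment, and the protocol does not say how the CRC stays blinded while doing it

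*Combined protocol and SAP*

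**What the plan says.** All references are to section 1.0, Protocol Synopsis.

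- **Study Design, on durability:** "To assess durability of responding RECELL-treated study areas at Week 52, the investigator and the CRC will confirm that ≥ 80% of the pigmentation" seen in the Week 24 photograph is still there. The task is limited to RECELL areas that responded, and the CRC is named as one of the two assessors.
- **Study Design, on the panel:** "Pigmentation of all study areas will be determined via centralized image interpretation by an expert dermatological panel blinded to treatment allocation".
- **Central Review Committee (CRC):** "The CRC will be blinded to the study site, treatment assignment, and the investigator's determination of repigmentation for each study area". No exception or end date is given.
- **Tertiary (Exploratory) Measures:** these include "CRC and investigator assessment of pigmentation for the study areas at Weeks 36 and 52", "CRC assessment of color matching for the study areas at Weeks 36 and 52" and, as a separate item, "Repigmentation durability at Week 52 as assessed by the investigator and CRC". None of the three is restricted to one arm.
- **Study Population:** roll-in subjects "will undergo the same study procedures and follow-up assessments as the pivotal cohort subjects".
- **Study Design, on later treatment:** RECELL may be offered for depigmented study areas after the Week 24 visit in non-responders and after the Week 52 visit in responders.

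The CRC's review rules are left to a charter that is not among the documents.

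**The concern.** A blinded panel cannot be asked to act on a set of areas picked by treatment without learning the treatment. A CRC member told to confirm durability of a responding RECELL area knows that area's assignment. With one area per arm in each subject, the member also knows that the other area is Control. The same members rate pigmentation and color match on both areas at Week 52, so those ratings would lose their blind too. The task is also framed as confirming a success, for one arm only.

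At stake is whether the Week 52 CRC results can be reported as blinded. The 80% durability threshold is not in question here.

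**Working it through.** **1. The plan's nearest figure.** The plan gives no figure for this point. Its planned size reproduces: 20 evaluable / (1 − 0.10) = 22.2, rounded up to 23.

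**2. Subjects whose allocation the request would reveal.** Inputs from Statistical considerations are 60% RECELL response, 20 evaluable, 23 planned and 46 maximum.
- 0.60 × 23 = 13.8, about 14, before dropout
- 0.60 × 20 = 12 evaluable
- 0.60 × 46 = 27.6, about 28, at the maximum size before dropout

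The 10% loss is the plan's only dropout figure. No further loss between Weeks 24 and 52 is assumed here.

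**3. What the photographs already suggest.** Suppose exactly one of a subject's two areas responded. With response rates *r* (RECELL) and *c* (Control) and areas assumed independent, the probability that it is the RECELL area is r(1−c) / [r(1−c) + c(1−r)].

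| RECELL rate | Control rate | Only RECELL responds | Only Control responds | Probability RECELL |
|---|---|---|---|---|
| 60% (plan) | 5% (plan) | 0.57 | 0.02 | 96.6% |
| 40% (assumed) | 5% | 0.38 | 0.03 | 92.7% |
| 30% (assumed) | 5% | 0.285 | 0.035 | 89.1% |
| 15% (edge of the margin) | 5% | 0.1425 | 0.0425 | 77.0% |
| 5% (no effect) | 5% | 0.0475 | 0.0475 | 50% |

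The 15% row reads the 10% margin as absolute points. At the planned rates the result depends on how often both areas respond. It is 0.60/0.65 = 92.3% if they never do, and 0.55/0.55 = 100% if every Control responder is in a subject whose RECELL area also responds. A RECELL-only request raises the probability to 100% in every row. At planned rates that adds 100 − 96.6 = 3.4 points (0 to 7.7 over the possible correlations). At 15% against 5% it adds 23 points, but to fewer subjects: 0.15 × 23 = 3.45. If both areas respond (0.60 × 0.05 = 3% under independence), response status gives no clue and the request would be the main one.

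**4. Can a Week 52 read precede another subject's primary read?** Week 52 is 52 − 24 = 28 weeks after Week 24. Subjects added after a sample-size increase are treated no earlier than the time when 11 subjects have 24-week data. Their Week 24 visits therefore fall at least 24 + 24 = 48 weeks after the last of those 11 was treated. A responder treated 52 − 48 = 4 or more weeks before that subject has by then reached Week 52. Roll-ins follow the same schedule and precede pivotal enrollment at their site. The order is feasible, but accrual and read timing are not given.

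**5. Reads needed under a masked scheme at 23 subjects** (areas independent, no dropout).
- RECELL responders only: 13.8
- All areas of all subjects: 46, so 46 − 13.8 = 32.2 extra
- Both areas of each subject with any responding area: 23 × (0.60 + 0.05 − 0.03) × 2 = 28.5, so 28.5 − 13.8 = 14.7 extra. This applies if every subject with no responding area drops out of the comparison, for instance by taking the RECELL option after Week 24.

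**The case against.** The strongest reply is that no section describes how images reach the readers or what labels they carry. The durability sentence may only name the analysis population. The CRC reads the study areas of both arms at Week 52 anyway, and the panel is said to be blinded. Masked reads with RECELL responders picked out later would fit that text, and the charter may say so. This stands to the extent that a broken blind is not established. It does not remove the conflict: the sentence gives the confirmation to the CRC rather than to the analyst, and durability is listed apart from the general Week 52 reads.

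A second reply is that at the planned rates the request tells readers little that a visible response does not. That is right at 60% against 5%. However, those rates are the effect under test, and blinding has to hold if the effect is small or absent. A guess from a photograph is also weaker than a stated assignment.

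Two stronger readings are tempting.
- A reader might infer that only RECELL responder images are sent to the CRC. That is an inference about workflow, which the documents do not describe.
- A reader might infer that the primary endpoint is compromised, for up to 23 of 46 subjects if the sample size is doubled. The documents do not support this. A subject's own primary read concerns Week 24, and subjects are randomized separately, so one subject's label does not reveal another's. The remaining route is readers learning what treated skin looks like. It needs unmasked Week 52 reads completed before later Week 24 reads. If all Week 24 reads were done first, the primary would be untouched.

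It is also true that Control areas still receive CRC pigmentation and color reads at Week 52, and that only about one Control responder is expected (0.05 × 23 = 1.15). The one-arm scope of the durability read therefore costs little information in itself.

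**Conclusion.** The point holds as a conflict between two statements in the synopsis: a CRC task defined by treatment, and a CRC blind without exception. The wording conflict is firm; its consequences are conditional. If the read is carried out as worded, both allocations become known for about 14 of 23 subjects (about 12 of 20 evaluable), assuming the planned 60% response. The CRC durability result and those subjects' Week 52 CRC pigmentation and color-match reads would then be unblinded. All are exploratory. Sample size, power and alpha are unaffected. Carry-over to later Week 24 primary reads is possible but not shown. The point is worth fixing because the same panel determines the primary endpoint and the remedy is cheap.

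**What to change.** Replace the CRC part of the durability sentence in Study Design, and match it in the CRC charter, along these lines:

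*At Week 52 the CRC compares the Week 24 and Week 52 photographs of both study areas for every subject who has both photographs and has had no RECELL treatment of a study area after Week 24. Areas are shown under masked codes in random order, with no indication of treatment or earlier responder status. Week 24 responders are selected and durability is summarised by arm at analysis. Each subject's Week 24 adjudication is locked before that subject's durability read. The same rules apply to roll-in subjects.*

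The restriction on later treatment is needed because the synopsis allows RECELL on study areas of non-responders after Week 24. Comparing every area regardless would mix in areas treated between the two photographs. The investigator's own durability assessment is not affected.

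**Cost:** about 15 to 32 extra side-by-side comparisons by the same readers at 23 subjects. At 46 subjects the range doubles to about 29 to 64. No new visits, photographs or readers are needed.

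**Limit:** masking stays imperfect where the treatment effect is visible. At planned rates a responding area is RECELL with probability 0.60/0.65 = 92% whatever the labels say. The change removes the stated assignment, not the visual clue.
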